6.2.3. Per-Protocol Population

The PP includes all randomized subjects who are eligible and have started their randomized treatment arm. Subjects with major protocol deviations as defined in the medical review plan are also excluded from the PP population.

Subjects who did not receive MRZ or TMZ, with or without RT are excluded from PP and SP.

Patients excluded from PP or SP will be reported in separate tables with the reason(s) of exclusion.

7. Subject Disposition

Subject disposition summary (number and percentage of subjects) will be presented on all subjects who are enrolled. The number of subjects will be summarized by investigator site and overall.

- Subjects who were enrolled
- Subjects who were screen failures
- Subjects who were randomized
- Subjects who took at least 1 dose of study drug (MRZ/TMZ)
- Subjects who discontinued the study drugs

Listing for screen failure reasons/ineligibility will be provided.

A summary of subject disposition will be presented by treatment arm for the following analysis populations:

- ITT
- SP
- PP

The number of subjects completing the study according to the protocol will be also displayed.

Reasons for **treatment discontinuation** will be summarized for all ITT subjects with the following categories:

- Completed
- Progressive disease (PD)/relapse/death due to PD
- Adverse events (AEs)
- Withdrawal by subject
- Physician's decision
- Protocol deviation
- Death
- Other malignancy
- Lost to follow-up
- Pregnancy
- Other (specify, including discontinuation of study drugs further to IDMC decision)

Reasons for **completing the study follow-up/study** (i.e. no more follow up visit and no longer participating in the study) will be collected on the eCRF and will be summarized for ITT subjects with the following categories:

- Death
- Lost to follow-up
- Withdrawal by subject
- Other (specify, including discontinuation of study drugs further to IDMC decision)

Listings will be provided for ITT subjects randomized but not treated, and for treated subjects who discontinued treatment with reason for treatment discontinuation highlighting discontinuation of study drugs further to IDMC decision.

8. Protocol Violations

The protocol violations were identified and assessed by clinical research physician or designee following EORTC standard operational procedure. The protocol violations will be summarized overall and by treatment arm in the ITT population and for the unmethylated MGMT stratum.

A listing of subjects with protocol violations will be provided.

9. Demographics And Baseline Characteristics

Summaries for the demographics and baseline characteristics will be summarized for the ITT population and by MGMT stratum (unmethylated, methylated and undetermined). Baseline clinical characteristics are defined as the latest data collected on or before Day 1 (or randomization day in case Day 1 is missing). When there are retested values, the retest values will be used for the analysis. Individual subject listings will be provided to support the tables.

9.1. Demographics and Baseline Characteristics

Demographic characteristics will be summarized using the following information from the Screening/Baseline Visit eCRF pages.

There will be no statistical comparison of demographic and baseline measurements between treatment arms.

At a minimum, the following continuous demographics and baseline characteristics will be summarized

- Age expressed in years (age = year of randomization – year of birth);
- Height expressed in cm;
- Weight expressed in kg; Body Mass Index (BMI) expressed in kg/m^2 (calculated via $\text{weight} / [\text{height}^2]$ where weight is expressed in kg and height in m); (BMI less than 19; BMI of 19 to less than 21; BMI of 21 to less than 23; BMI of 23 or greater);
- Body surface area (BSA), expressed in m^2 (set to BSA captured in the eCRF, otherwise calculated based on Dubois' methods, ie, $0.007184 * \text{height}^{0.725} * \text{weight}^{0.42}$, where height is expressed in cm and weight in kg if BSA missing in the eCRF);
- Clearance, calculated based on the Cockcroft Gault formula, where creatinine clearance (CrCl) (mL/min) = $(140 - \text{age}) (\text{weight} [\text{kg}] / 72 (\text{serum creatinine} [\text{mg}/\text{dL}]))$; for females, the formula is multiplied by 0.85) (Cockcroft, 1976);
- Relevant vital signs, i.e. systolic blood pressure, diastolic blood pressure and pulse rate;
- Mini mental state examination (MMSE) total raw score;

At a minimum, the following categorical demographics and baseline characteristics will be summarized:

- Age categories expressed in years (≤ 55 , >55) and (≤ 65 , >65);
- Sex (Female, Male);
- Ethnicity (Hispanic or Latino, Not Hispanic or Latino, Not reported);
- Race (American Indian or Alaska native, Asian, Black or African American, Native Hawaiian or Other Pacific Islander, White, Multiple, Other, Not reported);
- Baseline Eastern Cooperative Oncology Group (ECOG) Karnofsky Performance Status (70/80, 90/100);
- Electrocardiogram (ECG): Normal, Abnormal Not Clinically Significant, Abnormal Clinically Significant or Missing).
- Mini mental state examination (MMSE) total raw score (≤ 27 , >27);
- Baseline steroid use (yes, no),
- Hematology & Biochemistry values,
- Adverse Events (Common Terminology Criteria for Adverse Events [CTCAE] grade) before start of treatment;

9.2. Disease Characteristics

At a minimum, the following categorical baseline disease characteristics will be summarized:

- Primary disease (MedDRA);
- MGMT methylation status (methylated, unmethylated, undetermined/invalid);
- World Health Organization (WHO) classification of tumor (GBM, isocitrate dehydrogenase [IDH] wildtype, GBM, IDH mutant, Giant Cell GBM, Epithelioid glioblastoma, GBM, not otherwise specified [NOS], Other, Unknown);
- Extent of surgical resection (Biopsy, Partial or subtotal resection, Gross total resection, Unknown);
- IDH 1/2 mutation (Absent, Present, Cannot be determined, Not done);
- IDH 1 R132H immune histochemistry (IHC) (Negative, Positive, Cannot be determined, Not done);
- 1p/19q deletion (1p/19q co-deletion, 1p only deleted, 19q only deleted, None detected, Cannot be determined, Not done);
- Tumor hemisphere (Left, Right, Both, Midline);
- Tumor localization (Frontal, Temporal, Parietal, Occipital, Multilobar, Central).
- KI-67/MIB1 percentage of positive nuclei

- Number of lesions observed

At a minimum, the following continuous baseline disease characteristics will be summarized:

- Time (weeks) from first pathological diagnosis to randomization
- Target lesions maximum diameter (cm)
- Time (weeks) from tumor resection to randomization
- Time between first pathological diagnosis or tumor resection which ever occur first and date of randomization (weeks)

There will be no statistical comparison of disease characteristics between treatment arms.

9.3. Medical History

Based on variables extracted from the medical history eCRFs the number and percentage of subjects in each of the following categories will be presented by treatment arm: Note that the conditions/diagnosis will be presented by Medical Dictionary for Regulatory Activities (MedDRA) system organ class (SOC) and preferred term (PT) by descending order of frequency and graded by CTCAE. Subjects reporting more than one condition/diagnosis will be counted only once for that condition/diagnosis.

- Non-malignant medical condition will be presented by SOC and PT. A similar summary will be generated for the currently active abnormalities only, by SOC and PT.
- Type of primary malignancy: will be presented using the American Joint Committee on Cancer (AJCC) classification instead of the MedDRA SOC;

For each medical condition, a listing with subject ID numbers will be provided.

There will be no statistical comparison of medical history between treatment arms.

9.4. Prior and Concomitant Medications

A prior medication is defined as any medication with an end date prior to the date of randomization and collected on the eCRFs. A concomitant medication is defined as any drug that started on the day of or after randomization, but not later than 35 days after the last protocol drug administration. Medications with a start date prior to the date of randomization and continuing after randomization are also classified as concomitant medications. A medication will also be considered a concomitant medication if one of the following three cases occur: (1) the start date is missing and the end date is either after or on the day of randomization; (2) the start date is not missing but not 35 days after the last protocol drug administration and the end date is missing; (3) both the start date and the end date are missing.

Subjects reporting the same medication generic name two or more times will be counted only once for that generic name.

For each prior or concomitant medication, a listing with subject ID numbers will be provided.

There will be no statistical comparison for the prior and concomitant medications between treatment arms.

9.4.1. Prior Medications

A summary showing the number and percentage of subjects who took prior medications will be presented by WHO therapeutic drug class and generic drug name and by treatment arm.

9.4.2. Concomitant Medications

A summary showing the number and percentage of subjects who took concomitant medications will be presented by WHO therapeutic drug class and generic drug name and by treatment arm.

10. Study Treatments And Extent Of Exposure

Study treatment and extent of exposure summaries will be provided for each drug based on the SP. Descriptive statistics will be provided for treatment duration, number of cycles, cumulative dose, dose intensity, and relative dose intensity by treatment arm.

10.1. Treatment Duration

Radiotherapy

Radiotherapy consists of a conventionally fractionated regimen delivering a total dose of 60 Gy in 30 fractions in 6 weeks, a fraction of 2 Gy once daily, 5 days per week. The RT duration (in weeks) is defined as $(\text{last RT dose date} - \text{first RT dose date} + 1) / 7$.

Chemotherapy

The treatment start date is the date of the first dose of study drugs (MRZ or TMZ). The treatment end date is the date on which the decision was made by investigator to discontinue subject's treatment. Whenever the treatment is given in cycles and the last planned day of treatment is not the last day of the cycle, the total duration of the treatment must account for this by adding the appropriate number of days to complete the last cycle.

Temozolomide is given on a daily basis for 6 weeks during RT (concomitant phase) and after a 4-week interval, TMZ is given on days 1-5 of a 28-day cycle (maintenance phase).

- The concomitant TMZ duration (in weeks) is defined as $(\text{last concomitant TMZ dose date} - \text{first concomitant TMZ dose date} + 1) / 7$.
- The maintenance TMZ duration (in weeks) is defined as $([\text{maintenance TMZ end date} - \text{maintenance TMZ start date}] + 1 + (28 - n)) / 7$ where n is the last day of administration of the last cycle, ie, Day 1, 2, 3, 4, or 5.

Marizomib is given on Days 1, 8, 15, 29, 36 for one cycle of 6 weeks during radiotherapy (concomitant phase) and after a 4-week interval, MRZ is given on days 1,8,15 of a 28-day cycle (maintenance phase).

- The concomitant MRZ duration (in weeks) is defined as $([\text{last concomitant MRZ end date} - \text{first concomitant MRZ start date}] + 1 + (42 - n)) / 7$.
- The maintenance MRZ duration (in weeks) is defined as $([\text{maintenance MRZ end date} - \text{maintenance MRZ start date}] + 1 + (28 - n)) / 7$, where n is the last day of administration of the last cycle, ie, Day 1, 8, or 15.

For subjects who are still on treatment at the time of study closure or clinical cutoff, the planned cycle length will be used to calculate the end date and for both drugs the treatment duration (in weeks) is defined as: $[\text{the study treatment end date} - \text{the first study drug start date} + 1] / 7$.

Descriptive statistics will be provided for treatment duration and total number of cycles by treatment arm.

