10.4. Relative Dose Intensity

Relative dose intensity is the dose intensity divided by the planned dose intensity.

The planned dose intensity is

$$\begin{aligned} & \text{Planned dose intensity}_{\text{Conc TMZ or MRZ}} \\ &= \frac{42 * 75 \frac{\text{mg}}{\text{m}^2} \text{ of TMZ or } 5 * 0.8 \frac{\text{mg}}{\text{m}^2} \text{ of MRZ}}{\text{Theoretical duration of one cycle (weeks)} = 6 \text{ weeks}} \end{aligned}$$

$$\begin{aligned} & \text{Planned dose intensity}_{\text{Main TMZ}} \\ &= \frac{(150 \frac{\text{mg}}{\text{m}^2} \text{ at cycle 1} + \sum_1^N (n - 1) * 200 \frac{\text{mg}}{\text{m}^2}) / N \text{ of TMZ}}{\text{Theoretical duration of one cycle (weeks)} = 4 \text{ weeks}} \end{aligned}$$

$$\begin{aligned} & \text{Planned dose intensity}_{\text{Main MRZ}} \\ &= \frac{3 * 0.8 \frac{\text{mg}}{\text{m}^2} \text{ of MRZ}}{\text{Theoretical duration of one cycle (weeks)} = 4 \text{ weeks}} \end{aligned}$$

Relative dose intensities will be categorized into < 60%, 60% to <80%, 80% to <90%, 90% to <110%, and \geq 110%, and frequency counts will be provided by treatment arm.

For RT, the (relative) dose intensity is not meaningful. The number of subjects with cumulative dose >90%, \leq 90% of the planned total dose (60 Gy) will be summarized by treatment arm.

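### SAP 10.1 defines treatment end as the stop-decision date, but its cycle-completion formulas are exact only for the last dose date, so relative dose intensity can read too low in patients who have stopped

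*SAP*

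**What the plan says.** SAP 10.1 contains one definition of when drug treatment ends: "The treatment end date is the date on which the decision was made by investigator to discontinue" the subject's treatment. It adds a general rule that, when the last planned dosing day is not the last day of a cycle, duration is extended by "adding the appropriate number of days to complete the last cycle".

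The phase-specific formulas, in days before division by 7, are:

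- Maintenance temozolomide (TMZ): (maintenance end - maintenance start) + 1 + (28 - n), "where n is the last day of administration of the last cycle, ie, Day 1, 2, 3, 4, or 5".
- Maintenance marizomib (MRZ): the same form, "where n is the last day of administration of the last cycle, ie, Day 1, 8, or 15".
- Concomitant MRZ: (end - start) + 1 + (42 - n), with n not defined.
- Radiotherapy and concomitant TMZ: first dose to last dose, both explicitly tied to dose dates, with no days added.

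Terms such as "maintenance MRZ end date" are not defined separately. SAP 10.3 divides cumulative dose by this duration. SAP 10.4 states: "Relative dose intensity is the dose intensity divided by the planned dose intensity", and sorts the result into classes cut at 60, 80, 90 and 110%. SAP section 3 puts these tables in both the primary and the long-term follow-up report.

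**The concern.** The (28 - n) term carries the duration from the last dosing day to the end of the 28-day cycle. It does this correctly only if the end date in the formula is that last dosing day. If the end date is a later stop decision, the days between last dose and decision enter once through the end date and again through (28 - n). The denominator is then too long, and dose intensity and relative dose intensity (RDI) are too low.

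A decision after the last dose is plausible. Protocol 6.2.2 places the pre-cycle assessments within 3 days before each cycle and MRI every 8 weeks, and Protocol 5.2 sets re-treatment criteria before each adjuvant cycle. A stop may therefore be decided at the end of a cycle whose doses were all given.

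The exposure tables are where a reader sees how much marizomib was delivered and whether temozolomide delivery was maintained. Patients who stop after few cycles are hit hardest, because a fixed gap weighs more in a short duration. The formula for patients still on treatment at cut-off has no (28 - n) term, so stopped and ongoing patients would follow different rules.

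**Working it through.** The SAP prints no resulting duration or RDI, so there is no plan figure to reproduce. The check applies its own formulas to a fully dosed patient with cycles on schedule.

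**Inputs**
- Planned maintenance MRZ: 3 x 0.8 mg/m² over 4 weeks = 0.60 mg/m²/week (SAP 10.4).
- TMZ: 150 mg/m² in cycle 1, then 200 mg/m², on 5 days per 28-day cycle (Protocol 5.1.2).
- n = 15 for MRZ and 5 for TMZ when fully dosed (SAP 10.1).
- Day of the last cycle on which the decision falls: not in the documents. This is an assumption, shown as a range.

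**Step 1, end date = last dose.** Over k cycles, the last dose is on day 28(k - 1) + n from start. Duration = 28(k - 1) + n + (28 - n) = 28k days. MRZ RDI = [2.4k/(28k/7)]/0.60 = 100% for every k. The formula is exact on this reading.

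**Step 2, end date = decision, g days after the last dose.** Duration = 28k + g, so RDI = 28k/(28k + g). RDI falls below 90% when g > 28k/9: 3.1 days at k = 1, 12.4 at k = 4, 15.6 at k = 5, 56 at k = 18.

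**Step 3, maintenance MRZ (RDI %, true value 100).** Decision day is counted from Day 1 of the last cycle.

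| Cycles k | Day 15 (g=0) | Day 21 (g=6) | Day 28 (g=13) | Day 29 (g=14) | Day 43 (g=28) |
|---|---|---|---|---|---|
| 1 | 100 | 82.4 | 68.3 | 66.7 | 50.0 |
| 2 | 100 | 90.3 | 81.2 | 80.0 | 66.7 |
| 3 | 100 | 93.3 | 86.6 | 85.7 | 75.0 |
| 4 | 100 | 94.9 | 89.6 | 88.9 | 80.0 |
| 5 | 100 | 95.9 | 91.5 | 90.9 | 83.3 |
| 8 | 100 | 97.4 | 94.5 | 94.1 | 88.9 |
| 9 | 100 | 97.7 | 95.1 | 94.7 | 90.0 |
| 18 | 100 | 98.8 | 97.5 | 97.3 | 94.7 |

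The correct class is 90 to <110%. It is missed by no one for Day 15, at k = 1 only for Day 21, at k = 1 to 4 for Day 28 or 29, and at k = 1 to 8 for Day 43.

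**Step 4, maintenance TMZ.** The gap is 28 - 5 = 23 days for a Day 28 decision and 24 for Day 29. With the 5 dosing days in the planned dose, k = 1 to 6 gives 54.9, 70.9, 78.5, 83.0, 85.9, 88.0% (Day 28) or 53.8, 70.0, 77.8, 82.4, 85.4, 87.5% (Day 29). All are below the correct class.

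The planned maintenance TMZ intensity printed in 10.4 has no factor of 5, although the concomitant TMZ and MRZ formulas beside it do carry their numbers of doses. For k = 3 and Day 28:
- Delivered: 750 + 2 x 1000 = 2750 mg/m² over 107/7 weeks = 179.9 mg/m²/week.
- Planned with 5 days: 2750/12 = 229.2, so RDI = 78.5%.
- Planned as printed, reading the sum as (N - 1) x 200: (150 + 400)/3/4 = 45.8, so RDI = 392.5%.
- Planned as printed, taking the sum literally: (150 + 600)/3/4 = 62.5, so RDI = 287.9%.

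For a Day 28 decision and k = 1 to 6, the first printed reading gives 275 to 440%. The literal sum gives 161 to 288% at k = 3 to 6 and 275 and 354% at k = 1 and 2. Every one falls in the top class.

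**Step 5, concomitant MRZ, all five doses, n taken as 36.** An end date on day 36 gives 36 + 6 = 42 days and 100%. An end date on day 42 gives 48 days and 42/48 = 87.5%.

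**The case against.** The strongest reply is that this is a loosely named term rather than a wrong formula. The decision date defines the end of the subject's treatment as a whole, paired with a start date that is the first dose of either drug. The formulas use other terms, specific to drug and phase. In the MRZ arm, TMZ may finish after six cycles while MRZ continues for twelve more (Protocol 5.2 and 5.3), so one decision date cannot serve as the TMZ end date. Since n is a day of administration, the last dose is the natural partner, and the general rule allows only the days needed to finish the cycle. On that reading Step 1 shows the formulas to be exact.

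Much of this stands: the last dose date is probably what was meant. But the text does not say so. Where the section means a last dose date, for radiotherapy and concomitant TMZ, it says it. The only end date it defines is the decision date, and a programmer could reasonably apply it.

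A reader might also infer that the concomitant TMZ formula is wrong because it stops at the last dose while concomitant MRZ is completed to 42 days. The documents do not support that. The completion rule applies when the last planned dosing day falls before the end of the cycle, which is true of MRZ (day 36) but not of daily TMZ over six weeks. Intensity while on drug is a defensible measure, and cumulative dose and duration are reported separately.

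**Conclusion.** The point holds as a mismatch between a stated definition and the formulas that use it. For stopped patients, applying the printed definition lowers the RDI of a fully dosed patient from 100% to 28k/(28k + g). The size rests on the assumed decision day, and is nil if the decision coincides with the last dose.

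Three stronger readings are tempting and are not supported:

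- **That fully dosed patients who stop are generally misclassified.** For MRZ with a decision on Day 28 or 29, only those with one to four cycles change class; five to eighteen cycles stay in the correct one.
- **That maintenance TMZ would appear under-dosed as the SAP stands.** On the printed 10.4 formula, patients with one to six cycles read 110% or more. The 54 to 88% range appears only once the five dosing days are restored. These are two separate errors in one calculation, and correcting either alone leaves TMZ RDI wrong.
- **That the treatment comparison is biased.** Both arms use the same TMZ formula. A between-arm distortion would need the arms to differ in decision timing or in cycles completed, and the documents give no such figures. OS, PFS and type I error control do not use these durations.

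What is affected is the set of descriptive exposure tables in both reports. SAP section 3 expects marizomib to be stopped by physician or patient decision after the IDMC review. Those stops postdate the 28 April 2020 cut-off, so they bear on the follow-up report.

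**What to change.** In SAP 10.1:

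- State that the end date in the (28 - n) and (42 - n) formulas is the date of the last administered dose of that drug in that phase.
- Define n for concomitant MRZ as the last day of administration within the six-week phase.
- Keep the investigator's decision date for disposition only.

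In SAP 10.4, include the five dosing days per cycle in the planned maintenance TMZ intensity, and write the later-cycle term so that it can only mean (N - 1) cycles at 200 mg/m². If the factor was lost in the copy reviewed and stands in the signed SAP, that part needs no change.

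With both changes, a fully dosed patient on schedule returns 28k days and an RDI of 100% for either drug at any number of cycles. This makes a simple programming test. The cost is SAP wording and programming. No new data are needed, since dose dates are already required for the other duration formulas.

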10.3. Dose Intensity

Dose intensity during the treatment is defined as the cumulative dose divided by the treatment duration. Dose intensity will be calculated separately for TMZ and MRZ.

The dose intensities of TMZ and MRZ per subject are defined separately for the concomitant and the maintenance phase. The dose intensities will be calculated as:

Dose Intensity_{Conc}

$$= \frac{\text{Cumulative dose of Conc TMZ/MRZ from 1st administration until end of RTX } \left(\frac{\text{mg}}{\text{m}^2}\right)}{\text{Treatment duration (weeks)}}$$

Dose intensity_{Main}

$$= \frac{\text{Cumulative dose of Main TMZ/MRZ since start of 1st maintenance TMZ cycle } \left(\frac{\text{mg}}{\text{m}^2}\right)}{\text{Treatment duration (weeks)}}$$

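### For patients still on treatment at the cut-off, SAP 10.1 runs treatment duration from the first study drug dose, so maintenance dose intensity computed as written is diluted by the roughly 10 weeks before maintenance

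*SAP*

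**What the plan says.** SAP 10.1 treats two groups of patients differently. Once treatment has ended, each drug has its own duration in each phase. The maintenance durations start at that drug's maintenance start date and add 28 − n days to complete the last cycle; for marizomib (MRZ) this is "where n is the last day of administration of the last cycle, ie, Day 1, 8, or 15", and for temozolomide (TMZ) n runs from 1 to 5. For patients whose treatment has not ended by the cut-off or by closure of the study, the section says "the planned cycle length will be used to calculate the end date and for both drugs the treatment duration (in weeks) is defined as". The expression after these words subtracts the date of the first study drug from the end date of treatment, adds 1 and divides by 7. That rule names no phase. The start date is set earlier in the section as the first dose of either drug, which is Day 1 of chemoradiation. The only general end-date definition is: "The treatment end date is the date on which the decision was made by investigator to discontinue subject's treatment".

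SAP 10.3 states: "Dose intensity during the treatment is defined as the cumulative dose divided by the treatment duration". It adds: "The dose intensities of TMZ and MRZ per subject are defined separately for the concomitant and the maintenance phase". The maintenance numerator is "Cumulative dose of Main TMZ/MRZ since start of 1st maintenance TMZ cycle". The denominator is simply treatment duration in weeks, with no phase attached.

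SAP 10.4 divides this by a planned intensity per 4-week maintenance cycle, for MRZ 3 × 0.8 mg/m² over 4 weeks. "Relative dose intensities will be categorized into" five bands: <60%, 60% to <80%, 80% to <90%, 90% to <110%, and ≥110%.

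**The concern.** For ongoing patients the numerator counts doses from one phase, while the only duration that SAP 10.1 spells out for them covers all phases. The ratio would then show under-dosing that did not happen. A drug that has already been completed would also keep accruing time while the other drug continues.

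The primary analysis report keeps the 28 APR 2020 cut-off (SAP 2) and presents all of section 10 (SAP 3). SAP 2 reports no evidence of survival benefit and substantial toxicity. Readers of such a trial will ask whether the drugs were delivered as planned, and the dose-intensity table is one of the places they will look.

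A related gap sits in the same section. The 28 − n term is right if the end date is the last administration, but the only end date defined is the day on which the investigator decides to stop.

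**Working it through.** The plan gives no figure to reproduce, so the check is direct arithmetic on SAP 10.1 to 10.4 for a patient who receives every planned dose on time.

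**Inputs**
- Time before maintenance: 6 weeks of chemoradiation plus a 4-week break = 10 weeks (SAP 10.1).
- Planned maintenance MRZ intensity: 3 × 0.8 / 4 = 0.6 mg/m² per week (SAP 10.4).
- Maximum maintenance cycles: 18 for MRZ; 6 planned and 12 tolerated for TMZ (SAP 5.1). MRZ continues alone for up to 12 cycles after TMZ (Protocol 5.3).

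**Off-treatment formulas, end date read as last administration.** Six MRZ cycles: the last dose falls on maintenance day 5 × 28 + 15 = 155. Duration = 155 + (28 − 15) = 168 days = 24 weeks. Dose = 6 × 2.4 = 14.4 mg/m². Intensity = 14.4 / 24 = 0.6, so the relative dose intensity is 100%. Eighteen cycles give 72 weeks and again 100%. These formulas behave as they should.

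**On-treatment rule as written.** At MRZ maintenance cycle k the duration is 10 + 4k weeks and the dose is 2.4k mg/m². Relative intensity = [2.4k / (10 + 4k)] / 0.6 = 4k / (4k + 10).

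| Cycle k | Duration (weeks) | MRZ relative dose intensity |
|---|---|---|
| 1 | 14 | 28.6% |
| 3 | 22 | 54.5% |
| 6 | 34 | 70.6% |
| 12 | 58 | 82.8% |
| 18 | 82 | 87.8% |

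Such a patient falls in the <60% band up to cycle 3, in 60% to <80% for cycles 4 to 9 (cycle 10 is 40/50 = 80.0%), and in 80% to <90% from cycle 10 to 18. Reaching 90% needs 4k ≥ 0.9(4k + 10), that is k ≥ 22.5, beyond the maximum of 18.

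**Sensitivity to the 10 weeks.** If radiotherapy ends on day 40, maintenance starts after 67 days (9.57 weeks) and cycle 18 gives 72 / 81.57 = 88.3%. To reach 90% at cycle 18 the lead-in would have to be at most 72/0.9 − 72 = 8 weeks.

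**TMZ.** Compared with its value on a phase-specific duration, TMZ maintenance intensity is multiplied by 4 × (TMZ cycles given) / (10 + 4k).
- Cycles 1 to 6, both drugs running: the same 4k/(4k + 10), identical in the two arms.
- Six TMZ cycles completed, MRZ continuing alone: 24/38 = 63.2% at cycle 7, 24/58 = 41.4% at cycle 12, 24/82 = 29.3% at cycle 18. A control patient who completed the same six cycles is off treatment and keeps a factor of 1.

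These are dilution factors. They equal the reported TMZ percentages only if the planned TMZ dose in SAP 10.4 counts five dosing days per cycle.

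**End date.** Take a compliant patient whose treatment is stopped by decision on Day 1 of planned cycle 3, maintenance day 57, after two full TMZ cycles. With the decision date in the formula, duration = 57 + (28 − 5) = 80 days. With the last administration (day 33) it is 33 + 23 = 56 days. The ratio is 56/80 = 70%.

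**The case against.** The strongest reply is that phase durations were plainly intended. SAP 10.3 says the intensities are separate by phase, and SAP 10.1 supplies a duration for each drug and phase. The on-treatment sentence begins by saying how to set a missing end date, and a line about descriptive statistics for treatment duration follows it, so it can be read as defining an overall duration only. A programmer who reads it that way produces no error. The intent is probably as described, but the SAP does not say so, and the rule is the only duration stated specifically for these patients.

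Four further objections limit what can be claimed:

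- **TMZ.** A reader might infer that no fully dosed maintenance patient can reach 90% for either drug. As the text reached us, the planned TMZ formula in SAP 10.4 has no factor of 5. Taken literally, TMZ at cycle 6 would come out between about 129% and 353%, depending on how the sum is read. The factor may have been lost in conversion from PDF. The 90% ceiling therefore stands for MRZ; for TMZ only the dilution factor does.
- **Arm difference.** A reader might infer a false TMZ loss throughout the MRZ arm. In cycles 1 to 6 the dilution is the same in both arms, and MRZ's own distortion shrinks as cycles accumulate. The arm-specific part needs a patient on MRZ alone who still counts as on treatment.
- **Numbers affected.** A reader might infer that much of the trial is affected. Protocol 1.1 gives 286 patients enrolled by 10 Jul 2019; if that means this trial, (616 − 286)/616 = 54% entered in the last 293 days (41.9 weeks). That is recent entry, not a count of patients on treatment. It ignores discontinuations and includes patients still in chemoradiation, whom the rule does not distort.
- **Concomitant phase and end date.** Concomitant intensity would also shrink under the rule (6/22 = 27% at cycle 3), but the concomitant TMZ formula uses dates already known, so this reading is the least plausible. Double counting from the decision date is likewise a possible reading only: the formulas refer to a maintenance end date, which is not itself defined as the decision date.

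Number of cycles, cumulative dose (SAP 10.2) and reductions, interruptions and delays (SAP 10.5) are reported separately and do not use this denominator.

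**Conclusion.** The point holds for the text as written. For ongoing patients SAP 10.1 and 10.3 pair a phase-specific dose with a duration from first study drug, and a fully dosed patient's maintenance MRZ relative dose intensity becomes 4k/(4k + 10), at most 87.8%. This assumes a 10-week lead-in and that SAP 10.3 takes its denominator from the on-treatment rule. TMZ is diluted equally in both arms through cycle 6. The extra loss in the MRZ arm is confined to patients continuing MRZ alone, for example to 24/58 of the true value at MRZ cycle 12 after six TMZ cycles.

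The consequence is limited to descriptive exposure tables, chiefly at the 28 APR 2020 cut-off, and should matter less at the long-term follow-up analysis. No survival, progression or adverse-event analysis depends on it. The undefined maintenance end date needs a definition; it is not an established error.

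**What to change.** In SAP 10.1 and 10.3, state that the phase- and drug-specific durations are the denominators for all patients. For ongoing patients, set the end of the current phase by completing that drug's current cycle with the planned cycle length (42 days concomitant, 28 days maintenance); a drug already finished keeps the end of its own last cycle. Keep the overall duration from first study drug only as a separate descriptive statistic.

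Define the maintenance TMZ and MRZ end dates in the 28 − n formulas as the date of last administration of that drug, and use the decision date for disposition only. In the same edit, confirm that the planned TMZ dose in SAP 10.4 counts five dosing days.

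A fully dosed ongoing patient then shows 4k/4k = 100% for MRZ at every cycle from 1 to 18. TMZ is also 100%, including during MRZ alone, if the planned dose counts five days. The cost is SAP wording and a small programming change; no new data are needed.
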